5.7 Schedule modifications

5.7.1 IMP (investigational medicinal products) schedule

Continuation of IMP treatment with suspected progression is permitted; *c.f.*, [Paragraph 5.7.2.4](#). Discontinuation from study treatment may result from any of the criteria listed in [Paragraph 5.7.2.3](#).

If required, subjects may receive IMP up to 3 days before or after the scheduled date. A cycle started more than 3 days after the intended dose date will be considered a delay. Subsequent dosing should be based on the actual date of administration of the previous drug cycle.

Subjects will be monitored for infusion reactions during IMP administration. If an acute reaction is noted, subjects will be managed according to [Paragraph 5.7.2.7](#). IMP doses may be interrupted, delayed, or discontinued as per requirement.

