7.4 Safety assessments

At baseline, a medical history will be obtained to capture relevant underlying conditions. The baseline examinations will include weight, height, ECOG status, blood pressure, heart rate, and temperature, and will be performed within 14 days prior to first dose. Baseline signs and symptoms are those that are assessed within 14 days prior to first dose of study drug. Concomitant medications including steroid dose will be collected within 14 days prior to first dose of study drug and through the study treatment period.

Baseline local laboratory assessments will be done within 14 days prior to first dose and will include the following serum/plasma assessments: Hb, HCT, WBC (including differential counting), platelets, liver factors (ALT, AST, ALP, LDH, GGT, total bilirubin, total albumin, INR), creatinine or urea, Na, K, Ca, Mg, phosphate, glucose, TSH, free T4, CEA, Ca19.9, and Ca125. Additionally, urine analysis will be done.

The following baseline local laboratory assessments should be done within 28 days prior to first treatment: hepatitis B and C testing, according to each Institution's SOP.

Pregnancy testing of WOCBP must be performed within 24 hours prior to Day 1 and then every 4 weeks.

While on study treatment, the same local laboratory assessments as those of baseline will be done within 3 days prior to each dose.

Subjects will be evaluated for safety and tolerability if they have received any study drug. Toxicity assessments will be continuous during the treatment phase and formally recorded at each new therapy cycle, and every 8 weeks during planned breaks from active study therapy, and should be done in person. Once subjects reach the survival follow-up phase, either in-person or documented telephone calls to assess the subject's status are acceptable.

AE and laboratory values will be graded according to CTCAE v4.0.

The start and stop time of the study therapy infusions will be documented.

Additional measures, including non-study required laboratory tests, will be performed as clinically indicated or to comply with local regulations. Laboratory toxicities (*e.g.*, suspected drug-induced liver enzyme evaluations) will be monitored during the follow-up phase via local laboratories until all study drug-related toxicities resolve, return to baseline, or are deemed irreversible.

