7.7.4 Withdrawal or discontinuation

When a subject discontinues or withdraws prior to trial completion, all applicable activities scheduled for the final trial visit will be performed at the time of discontinuation. Any AE which are present at the time of discontinuation will be followed in accordance with the safety requirements outlined in [Chapter 8](#).

Subjects may withdraw consent at any time for any reason or be dropped from the trial at the discretion of Clinical Investigator should any untoward effect occur. In addition, a subject may be withdrawn by Clinical Investigator or Sponsor if enrolment into the trial is inappropriate, the trial plan is violated, or for administrative and/or other safety reasons. A subject must be discontinued from the trial for any of the following reasons:

- AE/SAE as specifically described.
- The subject withdraws consent.
- Confirmed disease progression; *c.f.*, [Paragraph 7.6](#).
- Any clinical AE, laboratory abnormality, or intercurrent illness which, in the opinion of Clinical Investigator, indicates that continued participation in the study is not in the best interest of the subject.
- Intercurrent illness that prevents further administration of treatment.
- Clinical Investigator's decision to withdraw the subject.
- The subject has a confirmed positive pregnancy test.
- Non-compliance with trial treatment or procedure requirements.
- The subject is lost to follow-up.
- Administrative reasons.

After the end of treatment, each subject will be followed for 30 days for AE monitoring. Subjects who discontinue for reasons other than PD/iCPD will have post-treatment follow-up for disease status until disease progression, starting a non-study cancer treatment, withdrawing consent, or becoming lost to follow-up. After documented disease progression, information on survival will be obtained until death, withdrawal of consent, or the end of the study, whichever occurs first.

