8.1.2 SAE (serious adverse events)

An SAE is any untoward medical occurrence that at any dose:

- Results in death.
- Is immediately life-threatening.
- Requires in-patient hospitalization or prolongation of existing admission.
- Results in persistent or significant disability or incapacity.
- Is a congenital abnormality or birth defect.
- Is an important medical event that may jeopardize the subject or may require medical intervention to prevent one of the outcomes listed above. Examples of such events include but are not limited to intensive treatment in an emergency room or at home for allergic bronchospasm, blood dyscrasias, or convulsions that do not result in hospitalization. Potential drug-induced liver injury (DILI) is also considered an important medical event (see Paragraph 8.7 for the definition of potential DILI).

Suspected transmission of an infectious agent (*e.g.*, pathogenic or nonpathogenic) via the study drug is an SAE.

Although pregnancy, overdose, cancer, and potential DILI are not always serious by regulatory definition, these events must be handled as SAE (see Paragraph 8.5 for reporting pregnancies).

Any component of a study end point that is considered related to study therapy (e.g., death is an end point; if death occurred due to anaphylaxis, anaphylaxis must be reported) should be reported as SAE.

Note:

The following hospitalizations are not considered SAE in this study:

- A visit to the emergency room or other hospital department for <24 hours which does not result in admission (unless considered an important medical or life-threatening event).
- Elective surgery planned prior to signing consent.
- Admission for a planned medical/surgical procedure.
- Routine health assessment requiring admission for baseline/trending of health status (e.g., routine colonoscopy).
- Medical/surgical admission other than to remedy ill health and planned prior to entry into the study. Appropriate documentation is required in these cases.
- Admission encountered for another life circumstance that carries no bearing on health status and requires no medical/surgical intervention (e.g., lack of housing, economic inadequacy, caregiver respite, family circumstances, administrative reason).
- Admission for administration of anti-cancer therapy in the absence of any other SAE.

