8.2 SAE (serious adverse events) collection and reporting

For nivolumab, the IB represents the reference safety information to determine expectedness of SAE for expedited reporting. For the FLOX regimen, the SmPC of each of the drug components represents the reference safety information. Following the subject's written consent to participate in the study, all SAE (in both study arms), whether related or not related to study drug, must be collected, including those thought to be associated with protocol-specified procedures. All SAE must be collected that occur during the screening period and within 100 days of the last dose of nivolumab. If applicable, SAE must be collected that relate to any later protocol-specified procedure.

Clinical Investigator must report any SAE that occurs after these time periods and that is believed to be related to any IMP or protocol-specified procedure, pertaining to the full duration of the study (c.f., Paragraph 7.8), which is in accordance with European Commission guidelines.

An SAE report must be completed for any event where doubt exists regarding its seriousness.

If Clinical Investigator believes that an SAE is not related to study drug, but is potentially related to the conditions of the study (such as withdrawal of previous therapy or a complication of a study procedure), the relationship must be specified in the narrative section of the SAE report form.

SAE, whether related or not related to study drug, and pregnancies, must be reported to Sponsor (or designee) within 24 hours of awareness of the event. SAE will be recorded on the Suspect Adverse Reaction Report form by the Council for International Organizations of Medical Sciences (CIOMS), c.f. Appendix 10. Pregnancies will be recorded on a Pregnancy Surveillance Form.

If only limited information is initially available, follow-up reports are required. All SAE must be followed to resolution or stabilization.

If an ongoing SAE changes in its intensity or relationship to study drug or if new information becomes available, the SAE report must be updated and submitted within 24 hours to Sponsor (or designee) using the same procedure used for transmitting the initial SAE report.

Sponsor's representative for SAE notifications has the following address:

[contact]

and

Cell Phone: ([contact]

Sponsor will immediately forward SAE notifications (in experimental arm patients) to the following address:

[contact]

or

Facsimile Number: (+1) [contact]

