8.3 Disease progression or recurrence

Disease progression can be considered as a worsening of a patient's condition attributable to the disease for which the IMP is being studied. It may be an increase in the severity of the disease under study and/or increase in the symptoms of the disease. Expected progression of the disease under the study and/or expected progression of signs and symptoms of the disease under study, unless more severe in intensity or more frequent than expected for the patient's condition, will not be reported as AE. Events which are definitely due to disease progression will not be reported as AE. However, if Clinical Investigator considers that there was a causal relationship between treatment with IMP or protocol design/procedures and the disease progression/recurrence, this will be reported as SAE.

Death due to progressive disease will be recorded on a specific form in the CRF and not as SAE. Any new primary cancer (non-related to the cancer under study) will be considered for reporting as SAE.

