### **3.3. Analysis populations**

The following study populations will be defined:

- **Intention-to-treat population:** Includes all randomized participants, regardless of protocol adherence. We expect about 5% of randomized patients to have non-MSS tumor. These patients will be excluded from the analysis post-randomization. According to Fergusson and co-workers [Fergusson et al., 2002], such exclusion does not introduce bias and may be legitimate if an independent, blinded adjudication committee makes the decision on exclusion after evaluating all randomized patients. Sample size calculations include necessary adjustments to preserve the same power after exclusion of misdiagnosed patients. The sample size calculation has included necessary adjustments to maintain the same power after exclusion of patients with non-MSS tumor.
- **Safety population:** Includes all randomized participants who have received at least one dose of study medication and had at least one sequential safety-related observation. Subjects who withdraw from the study will be included in the safety analysis given the safety population criteria are otherwise met. A list of withdrawn subjects, preferably with the reasons for withdrawal, will be made.
- **Per-protocol population:** Includes all subjects who have adhered to all protocol-defined treatments and outcome assessments.

We will account for all of the patients registered in the study. The number of patients who are not evaluable, or who die or withdraw before treatment has begun, will be specified. The distribution of follow-up time will be described and the number of patients lost to follow-up will be given. Start of follow-up will be defined as the date of randomization.

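### The safety population adds an undefined post-dose observation condition that protocol 7.4 does not have, so a treated patient can be left out of the safety analysis

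*SAP*

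**What the plan says.** SAP 3.3, in wording identical to protocol 10.3, gives the safety population two conditions: "Includes all randomized participants who have received at least one dose of study medication and had at least one sequential safety-related observation". Protocol 7.4 gives one: "Subjects will be evaluated for safety and tolerability if they have received any study drug". The protocol therefore differs from itself, and the SAP carries over the narrower rule.

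Both population sections add a sentence on withdrawals: "Subjects who withdraw from the study will be included in the safety analysis given the safety population criteria are otherwise met". It keeps withdrawn patients only when the same two conditions are satisfied. Neither document says what kind of observation qualifies, by when it must occur, or whether it must be a scheduled visit.

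The accounting paragraph in both documents promises counts of patients who are not evaluable, or who die or withdraw before treatment starts. It does not name patients who die or are lost after the first dose. SAP 4.4 does promise the number and timing of withdrawals and losses to follow-up.

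**The concern.** A safety population is normally fixed by exposure, which is known once the first dose is given. The second condition here depends on what happens afterwards, and what happens afterwards may be the toxicity being counted. The sentence on withdrawals does not remove the problem, because it refers back to the same conditions.

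Safety and tolerability matter in this trial. Protocol 3 and SAP 2.1 list them among the aims on which superiority is to be investigated, and SAP 5.2 compares them between arms by chi-squared or Fisher's exact test. Both the numerator and the denominator of those proportions depend on who is in the population. With about 50 patients per arm, one early fatal event can be the only one in its arm.

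**Working it through.** The plan states no figure for the safety population, so there is none to reproduce. The sample size is not affected by this point. The check is a comparison of texts, followed by a small illustration.

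**Step 1: what the clause removes.** Protocol 7.4 covers all treated patients. Protocol 10.3 and SAP 3.3 cover treated patients who also have a qualifying observation. The difference is the treated patients without one.

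**Step 2: what could qualify under the documents.**

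- Monitoring at dosing (protocol 5.7.1): "Subjects will be monitored for infusion reactions during IMP administration". If this counted, every treated patient would qualify and the clause would exclude nobody. The word sequential suggests something that follows the dose.
- Second dosing day: FLOX is given on days 1 and 2 (protocol 5.4), and vital signs are taken before each dose (protocol 7.5.3).
- Next cycle: adverse events are formally recorded at each new cycle and cycles are two weeks apart, so the next scheduled visit is day 1 + 14 = day 15, within 3 days. The same sentence of protocol 7.4 says that toxicity assessment is continuous.
- Death: the SAE definition includes an event that "Results in death" (protocol 8.1.2), and protocol 8.2 says "all SAE (in both study arms), whether related or not related to study drug, must be collected". Protocol 8.3 makes an exception: "Death due to progressive disease will be recorded on a specific form in the CRF and not as SAE".
- Leaving the trial (protocol 7.7.4): "all applicable activities scheduled for the final trial visit will be performed at the time of discontinuation". The flow chart has a withdrawal visit with adverse event review.

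**Step 3: outcome by type of patient.**

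| Patient after first dose | Protocol 7.4 | Protocol 10.3 and SAP 3.3 |
|---|---|---|
| No later contact of any kind | Included | Excluded |
| Dies before next cycle, reported as SAE | Included | Included if the SAE report counts |
| Dies before next cycle, attributed to progression | Included | Unclear, as this death is not an SAE |
| Leaves, withdrawal visit done | Included | Included if that visit counts |

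**Step 4: size.** Inputs: 50 patients per arm (protocol 4.2), all assumed treated; k patients dropped from one arm (assumed 1 to 3); x other patients in that arm with a grade 3–5 event (assumed 15). Each dropped patient is 1/50 = 2 percentage points.

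- If the dropped patients had an event, the full rate is (x + k)/50 and the reported rate is x/(50 − k).
- If they had none, the full rate is x/50 and the reported rate is again x/(50 − k).

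| k | Dropped patients had an event: full, then reported | Dropped patients had no event: full, then reported |
|---|---|---|
| 1 | 16/50 = 32.0%, 15/49 = 30.6% | 15/50 = 30.0%, 15/49 = 30.6% |
| 2 | 17/50 = 34.0%, 15/48 = 31.3% | 15/50 = 30.0%, 15/48 = 31.3% |
| 3 | 18/50 = 36.0%, 15/47 = 31.9% | 15/50 = 30.0%, 15/47 = 31.9% |

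With x = 20 and k = 1 to 3 dropped patients who had events, the rates go from 42.0%, 44.0% and 46.0% to 20/49 = 40.8%, 20/48 = 41.7% and 20/47 = 42.6%.

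For a fatal event that no other patient in the arm has, a true 2%, 4% or 6% would be reported as 0/49, 0/48 or 0/47. Fisher's exact p for k/50 against 0/50 is 1.00, 0.49 and 0.24 for k = 1, 2 and 3. What is lost is an event from the table; the test would not have been significant in any of these cases.

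**The case against.** The strongest counter-argument concerns the consequence. A reader might infer that any patient who dies or leaves straight after the first dose automatically drops out of the safety analysis. The documents do not say so. They ask for an observation and do not require a scheduled visit. Assessment is continuous, SAEs including deaths must be collected in both arms, and a patient who leaves should have final-visit activities. Any of these can supply the observation. This stands: exclusion is firm only for treated patients with no later contact.

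It also stands that the direction of bias is not fixed. A patient with no later contact usually has no known event, so dropping that patient raises the reported rate slightly. Early deaths remain visible elsewhere: protocol 7.6.7 classifies deaths within 30 days of randomization, including those from toxicity, and deaths count in PFS and OS. SAP 5.2 does not say that its SAE summaries are limited to the safety population. The first two cycles are FLOX in both arms, so losses before day 15 come before any nivolumab, and the lack of safety data on the new sequence carries less weight in that window.

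Finally, protocol 7.4 is a section on procedures, while 10.3 and SAP 3.3 define populations and agree with each other. That is fair, but 7.4 still says whose safety will be evaluated, and its answer differs.

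These points limit the size of the problem but give no reason to keep the clause. Read generously, it excludes almost nobody and does no work. Read strictly, it selects on what happens after dosing, in a trial where the sites know the assignment.

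**Conclusion.** The inconsistency is real, and the observation condition should go. Treated patients with no later contact are excluded by the rule as written. Those who die or leave before the next cycle may be excluded, depending on an undefined term, and deaths attributed to progression are the least clear case.

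The expected effect is small: 2 percentage points of an arm per patient, assuming 50 treated per arm. The reported rate moves down if the excluded patient had an event and up if not. The values of k and x above are illustrations. The documents give no rate of early unobserved loss, so no probability that an arm loses a patient can be supported.

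A reader might also infer that, once the clause is gone, every early death becomes a grade 5 adverse event. That does not follow, because protocol 8.3 keeps death due to progressive disease off the SAE form.

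**What to change.** In protocol 10.3 and SAP 3.3, define the safety population as all randomized patients who received at least one dose of any study drug, in line with protocol 7.4, and delete the observation clause. The condition in the sentence on withdrawn patients then reduces to having been treated.

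Add one line to the patient accounting: the number of treated patients in each arm with no later safety observation.

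Count deaths after dosing under the existing SAE rules, with deaths due to progressive disease handled as in protocol 8.3.

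The cost is one deleted clause in each document and one added count. No new data are needed, since the count comes from visit, adverse event and follow-up records that are already planned.

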## **4. Trial Populations**

### **4.1. Screening data**

Data on subjects who do not meet the eligibility criteria will not be recorded.

### **4.2. Eligibility**

Eligible patients, with no upper age limit to recruit subjects reflecting population-based incidence rates, have previously untreated, unresectable metastatic colorectal MSS adenocarcinoma. Essential study inclusion criteria are age  $\geq 18$  years, measurable infradiaphragmatic (liver, peritoneal and/or nodal) metastatic manifestation(s) according to Response Evaluation Criteria in Solid Tumors version 1.1 (RECIST 1.1), and Eastern Cooperative Oncology Group performance status 0-1. In addition, C-reactive protein (CRP)  $<60$  mg/L is required at study entry. A period  $<6$  months since discontinuation of neoadjuvant or adjuvant oxaliplatin-containing chemotherapy and a history of autoimmune disease are main exclusion criteria. The complete list of inclusion and exclusion criteria can be found with the clinical trial registration (ClinicalTrials.gov Identifier: NCT03388190) and in the trial protocol.

### **4.3. Recruitment**

This information will be reported in a CONSORT flow diagram of the study cases.

### **4.4. Withdrawal / Follow-up**

The number of subjects that withdraw consent or are lost to follow-up, with timing of such events, will be reported.

#### 4.5. Baseline patient characteristics

Continuous baseline characteristics will be presented as means and standard deviations or as medians and minimum and maximum dependent on the distribution. Categorical data will be presented by frequencies and percentages. Baseline characteristics will be presented by intervention and control groups. Following characteristics will be presented: age, sex, ECOG performance status, primary tumor sidedness, tumor (K)RAS/BRAF mutation status, number of metastatic sites, and if the liver is involved or not.

### 5. Analysis

#### 5.1. End point definitions

*Primary end point:* PFS; radiologic assessment every 8 weeks, according to the Response Evaluation Criteria in Solid Tumors (RECIST) and the RECIST consensus guideline for assessment of response to immune-modulating therapies, iRECIST.

*Secondary end points:*

Safety: incidence of adverse events (AE), as reported according to Common Terminology Criteria for Adverse Events (CTCAE) version 4.0 recorded on ongoing basis.

Tolerability: AE grading, as assessed by CTCAE v4.0 recorded on ongoing basis.

ORR: the percentage of patients with a confirmed complete response (CR) or partial response (PR).

DOR: the time from the first documentation of a CR or PR to disease progression.

SSCRR: the percentage of patients with a confirmed resection of metastatic disease with microscopically free margin (R0).

OS: the time from randomization to death of any cause.

QoL: assessment undertaken at study enrolment, completion of the active therapy of the first treatment sequence (after 16 weeks), and disease progression, using the consensus modules EORTC QLQ-C30, EORTC QLQ-CIPN20, and EQ-5D-5L.

*Tertiary end point:* Cost estimate; evaluation of the healthcare costs (relating to the sequencing procedures and administered medication) and health effects (quality-adjusted life years), expressed as incremental cost-effectiveness ratio, of the sequential therapy relative to the control group as comparator.

*Exploratory end points:* Various analyses will be undertaken for exploratory end points listed in 1.2.

